## Pharmacokinetic Parameters

PK parameters will be derived from the plasma nicotine baseline-adjusted concentrations versus time profiles using a NCA, with Phoenix WinNonlin 6.3 (Model 200-202, extravascular). The following PK parameters will be calculated for controlled and uncontrolled use:

PK Parameter	Definition
$C_{max(\text{controlled})}$	Maximum measured plasma nicotine concentration during the Controlled Use Session
$C_{max(\text{uncontrolled})}$	Maximum measured plasma nicotine concentration during the Uncontrolled Use Session
$AUC_{(\text{controlled})}$	Area under the nicotine concentration-time curve calculated using linear trapezoidal summation from time zero (defined as the start of controlled use) to 180 minutes (or the last quantifiable concentration during that interval)
$AUC_{(\text{uncontrolled})}$	Area under the nicotine concentration-time curve calculated using linear trapezoidal summation from time 360 (defined as the start of uncontrolled use) to 540 minutes (or the last quantifiable concentration during that interval)
$T_{max(\text{controlled})}$	Time of the maximum measured plasma nicotine concentration during the Controlled Use Session
$T_{max(\text{uncontrolled})}$	Time of the maximum measured plasma nicotine concentration during the Uncontrolled Use Session
$K_{el(\text{controlled})}$	Apparent first-order terminal nicotine elimination rate constant calculated from a semi-log plot of the plasma concentration-time curve of the Controlled Use Session
$K_{el(\text{uncontrolled})}$	Apparent first-order terminal nicotine elimination rate constant calculated from a semi-log plot of the Uncontrolled Use Session

$T_{1/2}(\text{controlled})$	Apparent first-order terminal nicotine elimination half-life calculated as $0.693/K_{\text{el}}$ of the plasma concentration-time curve from time zero (defined as the start of controlled use) to 180 minutes
$T_{1/2}(\text{uncontrolled})$	Apparent first-order terminal nicotine elimination half-life calculated as $0.693/K_{\text{el}}$ of the plasma concentration-time curve from time 360 (defined as the start of uncontrolled use) to 540 minutes

Actual sampling times (relative to the corresponding administration time), will be used for calculation of PK parameters. In the case where less than 3 consecutive measurable concentrations are observed, AUC will not be estimated for that profile.

The trapezoidal rule (linear trapezoidal linear interpolation) will be used to estimate the area under the curve, and the terminal phase will be estimated by maximizing the coefficient of determination estimated from the log-linear regression model. However,  $t_{1/2}$  and  $K_{\text{el}}$  will not be estimated for individual concentration-time profiles where the terminal log-linear phase cannot be reliably characterized (log linear terminal phase with  $R^2$  of at least 0.8 and using minimum of three data points not including  $C_{\text{max}}$ ).

Plasma nicotine PK parameters will be summarized by treatment using the following descriptive statistics N, min, arithmetic mean, median, max, SD and CV%.

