5. INTRODUCTION

5.1. Background

With the introduction of the 2009 Family Smoking Prevention and Tobacco Control Act, the Food and Drug Administration (FDA) was granted the authority to regulate tobacco products including the nicotine content of cigarettes. In July 2017, FDA Commissioner [name]., announced the FDA's intention to limit nicotine in cigarettes to minimally or non-addictive levels. During his announcement, [name] stated that it has long been known that nicotine is the primary addictive component of cigarettes and that if smokers lose their addiction to cigarettes, they will be free to choose when and how often to smoke. A key component in the FDA's announced plan is to provide current smokers who are unable or unwilling to quit using nicotine with other, less harmful, means to obtain it. In other words, to provide a migration route away from traditional cigarettes to other types of tobacco or nicotine products such as cigarettes based on heat not burn technology, traditional smokeless, Snus, or electronic nicotine delivery system (ENDS) products.

Historically, tobacco harm reduction initiatives have focused on efforts to prevent or reduce tobacco initiation rates, increase quit rates, and decrease recidivism. The proposed reduction of nicotine cigarettes is believed to represent a viable policy tool to impact cigarette initiation rates and cigarette quit rates. Studies conducted to date indicate that reducing the nicotine content of cigarettes to non-addictive levels would potentially limit the reinforcing effects of cigarettes. A number of recent studies suggests that cigarettes with very low nicotine (VLN) content are associated with a positive set of outcomes, including reductions in the number of cigarettes smoked, reductions in nicotine exposure and nicotine dependence, increased abstinence from smoking, reduced exposure to toxicants, and fewer adverse events (AEs) (Rupprecht et al., 2017; Donny et al., 2007; Donny et al., 2015; Benowitz et al., 2007; Benowitz et al., 2009; Benowitz et al., 2012; Hatsukami et al., 2013). These studies evaluated cigarettes with nicotine content ranging from 0.4 to 15.8 mg nicotine per gram of tobacco with the typical combustible cigarette tobacco content ranging from approximately 8 mg to 20 mg.

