**Pharmacokinetic Population:**

All subjects who use any study product and have pre- and at least one post-use plasma concentration value for the Controlled Use Session of Part B. The PK Population will be used for statistical analyses of the PK parameters.

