### Methods for Handling Missing Data

No imputation of values for missing data will be performed. All data recorded on the case report form will be included in the listings that will accompany the clinical study report. Missing pharmacodynamic data, including reasons for the missing data, will be listed by subject and examined on a case-by-case basis to determine if these affect subject allocation.

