## Pharmacokinetic

### Concentration Data

Nicotine plasma concentrations produced by the administration of the study products will be determined to establish the PK profile of each treatment.

Concentrations that are below the limit of quantitation (BLQ) will be treated as zero for descriptive statistics.

Nicotine baseline adjusted concentration will be calculated as follows: post-use concentration – pre-use concentration.

Descriptive statistics will be calculated at each individual time point. Plasma concentration data (both unadjusted and baseline-adjusted) will be summarized by treatment using the following descriptive statistics: number of non-missing values (N), minimum (min), arithmetic mean, median, maximum (max), standard deviation (SD) and coefficient of variation (CV%).

The individual plasma concentration/time profiles will be presented using the actual sampling times whereas the mean plasma concentration/time profiles ( $\pm$ SD) will be presented using the nominal sampling times. Concentration profiles will be presented on both linear and semi-log scales.

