#### Statistical Analysis of PK Parameters

A linear mixed model for analysis of variance (Proc Mixed) will be performed on the baseline-adjusted log transformed nicotine PK parameters in Part B ( $C_{\text{max}}(\text{controlled})$ ,  $C_{\text{max}}(\text{uncontrolled})$ ,  $AUC_{(\text{controlled})}$  and  $AUC_{(\text{controlled})}$ ). The model will include sequence, study product, and period as fixed effects and subject nested-within sequence as a random effect. Sequence will be tested using subject nested-within sequence as the error term. From each model, the geometric LSM and 95% confidence intervals will be calculated for each study product. Separate analyses will be performed on the parameters calculated for the Controlled and Uncontrolled Use sessions. Geometric mean ratios for each pair comparison, 95% confidence interval and p value will be provided.

The SAS codes for the model will be as follows:

```
Proc MIXED data=test;
  class subject sequence period product;
  model log(Cmax0_180) = sequence period product / ddfm=KR;
  random subject (sequence) / type=UN;
  estimate "Product A vs Product B" product 1 -1 0 /cl alpha=0.05;
  estimate "Product A vs Product C" product 1 0 -1 /cl alpha=0.05;
  estimate "Product B vs Product C" product 0 1 -1 /cl alpha=0.05;
  lsmeans product/cl alpha=0.05;
run;
```

The Hodges-Lehmann's method will be used to estimate the median differences and the 95% confidence interval of  $T_{\text{max}}$  and  $T_{1/2}$  between the products for controlled and uncontrolled use.

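### The SAP departs undeclared from the protocol on unadjusted PK parameters and Completers, and its AUC and log rules can drop the lowest-exposure VLN profiles from the PK ratio

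*SAP*

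**What the plan says.** **Parameters.** The protocol (Synopsis, Pharmacokinetics; 12.4.4) requires derived PK parameters to be summarised both without and with baseline adjustment. SAP 9 derives them from baseline-adjusted concentrations only. Tables 14.2.1.3.1-6 and Listing 16.2.6.3.3 are likewise adjusted only; unadjusted results are planned for concentrations alone.

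**Completers.** Protocol 12.3 requires pharmacodynamic and PK data in the Controlled Use Session of Part B. SAP 5 repeats this, then requires PK parameters in each of the three periods, without saying which parameters count.

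**Declared changes.** Protocol 12.1 says that the SAP will carry any amendments to the proposed analyses. SAP 12 says there are none.

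**BLQ, adjustment and log.** SAP 9 says: "Concentrations that are below the limit of quantitation (BLQ) will be treated as zero for descriptive statistics". For the adjustment it says "Nicotine baseline adjusted concentration will be calculated as follows", namely post-use minus pre-use, with no rule for a negative result. On AUC it says: "In the case where less than 3 consecutive measurable concentrations are observed, AUC will not be estimated for that profile". It does not say whether measurable refers to raw or adjusted values. The ratio analysis uses the statement "model log(Cmax0_180) = sequence period product / ddfm=KR", and the AUCs are analysed on the log scale in the same way. SAP 6 adds: "No imputation of values for missing data will be performed".

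**PK Population.** SAP 5 requires only that subjects use a product and "have pre- and at least one post-use plasma concentration value for the Controlled Use Session of Part B".

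**The concern.** A profile that fails the AUC rule, or whose adjusted Cmax or AUC is at or below zero, leaves the log model because exposure was low. The subject nevertheless belongs to the population said to be analysed. VLN is the likeliest product to be affected. It contains 0.4 mg nicotine per gram, and Protocol 5.1 describes the studied cigarettes "with the typical combustible cigarette tobacco content ranging from approximately 8 mg to 20 mg". Losing the lowest VLN Cmax values raises the VLN/own-brand ratio and so understates the difference that the secondary objective is meant to measure.

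The Completer wording carries the same mechanism into a pharmacodynamic analysis. If PK parameters is read to include AUC or half-life, a fully compliant subject could leave the sensitivity analysis of both primary endpoints because VLN delivered little nicotine.

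The missing unadjusted parameters are a plain conflict between the documents. They also remove the output that does not depend on the pre-use subtraction.

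**Working it through.** **1. Text comparison (no assumption needed).**

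| Item | Protocol | SAP |
|---|---|---|
| Parameter summaries | unadjusted and adjusted (Synopsis; 12.4.4) | adjusted only (9; Planned Tables; Planned Listings) |
| Completer PK condition | PK data (12.3) | PK parameters, all three periods (5) |
| Declared changes | amendments to appear in the SAP (12.1) | none (12) |

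**2. Inputs.** Planned completers: 54 (SAP 4). That number comes from the urge endpoint: a paired t test with difference 15.85 and SD of the difference 28.44 x sqrt(2) (zero within-subject correlation) gives n = 53, and 81.1% power at 54. There is no stated figure for the PK comparison to reproduce. Nicotine content: 8/0.4 = 20 and 20/0.4 = 50, so VLN has 20 to 50 times less if both figures are per gram. The documents give no LLOQ and no expected VLN concentrations, so everything below rests on assumptions.

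**3. Size if low VLN Cmax values are lost.** Sequences ABC/BCA/CAB, N = 54, log-normal Cmax with log-scale variance ln(1 + CV^2). The model has fixed sequence, period and product and random subject, fitted by generalised least squares with known variances. The lowest k VLN values are removed: 3/54 = 5.6%, 5/54 = 9.3%, 11/54 = 20.4%. Inflation of the VLN/own-brand ratio:

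| CV | Within-subject correlation | k = 3 | k = 5 | k = 11 |
|---|---|---|---|---|
| 50% | 0.2 | 1.051 | 1.080 | 1.164 |
| 50% | 0.4 | 1.043 | 1.068 | 1.137 |
| 50% | 0.6 | 1.030 | 1.047 | 1.094 |
| 100% | 0.2 | 1.093 | 1.147 | 1.309 |
| 100% | 0.4 | 1.075 | 1.119 | 1.248 |
| 100% | 0.6 | 1.055 | 1.087 | 1.176 |

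The worst cell, applied to a true ratio of 0.20, gives 0.20 x 1.309 = 0.26; applied to 0.05 it gives 0.065.

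The pull can also go the other way. With complete data the contrast is a difference of simple log means, so one retained adjusted value at a tenth of its true level multiplies the ratio by 0.1^(1/54) = 0.958, and three by 0.1^(3/54) = 0.880.

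**4. How often.** Profiles were simulated at the 14 post-use times of the controlled session. Assumptions: half-life 90-150 minutes, peak at 5-10 minutes, assay noise 5-15%, CV 50-100%, no pre-use residual. Share of VLN profiles lost, by geometric-mean VLN peak:

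| VLN peak | Cmax | AUC | Fewer than 3 points after Cmax (half-life) |
|---|---|---|---|
| 2 x LLOQ | 4-20% | 9-28% | 11-37% |
| 4 x LLOQ | 0-5% | 0-8% | 0-13% |
| 10 x LLOQ | under 1% | under 1% | up to 1.3% |

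The half-life column is a lower bound, because the R-squared rule was not applied. Reading the peak as an arithmetic mean raises the losses: at 2 x LLOQ to 6-34% (Cmax) and 13-44% (AUC).

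**5. Completers.** 54 times the fractions in step 4. AUC reading at 2 x LLOQ: 54 x 0.086 = 5 to 54 x 0.283 = 15; at 4 x LLOQ, 0 to 4. Half-life reading: 6 to 20, and 0 to 7. A Cmax-only reading need exclude none.

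**The case against.** Four objections have force.

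*BLQ is nearly specified.* Zero is set for descriptive statistics, and these cover the adjusted concentrations that feed the parameters. Trailing BLQ samples are covered by ending AUC at the last quantifiable value. A reader might infer that BLQ is unhandled in the non-compartmental analysis. That goes too far: the value is close to implied and needs only a sentence. What stands is that the AUC rule and the log remove whole profiles because exposure was low.

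*The conclusion is safe.* A reader might infer that the ratio could mislead about whether VLN exposure is lower. The figures do not support that for Cmax. A factor of about 1.3 would not reverse a five-fold or larger difference, and this bias runs against the test product. The largest figure needs 20% loss, CV 100% and correlation 0.2 together, and loss near 20% needs a typical VLN peak only about twice the LLOQ.

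*Losses can be traced.* The SAP promises: "Plasma nicotine PK parameters will be summarized by treatment using the following descriptive statistics N, min, arithmetic mean, median, max, SD and CV". Listing 16.2.6.3.3 shows each subject's adjusted parameters. Losses are therefore not hidden. However, the Tables 14.2.2.1.1-3 shell gives no n, and N for Cmax may count zeros that the log cannot use.

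*The Completer text is clarification.* Protocol 12.1 lets the SAP add detail on populations, and the SAP does not demand an estimable AUC or half-life. A reader might infer that compliant subjects will be excluded; the text only permits that reading. Replacing data by parameters can still change who qualifies, so the wording should be settled.

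None of these answers the missing unadjusted parameter summaries.

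**Conclusion.** The point holds, with minor to moderate severity. Two parts rest on the text alone: the unadjusted parameter summaries required by the protocol are absent from the SAP, and the Completer PK condition was reworded, while SAP 12 declares no change. The effect of the Completer wording depends on how it is read. It touches only a sensitivity analysis of the two primary endpoints; the primary Pharmacodynamic Population is unaffected.

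The third part, exposure-dependent loss from the ratio analysis, follows from the stated rules, but its frequency is unknown and may be nil. If the lowest 5-20% of VLN Cmax values were lost, the VLN/own-brand ratio would be inflated about 1.03- to 1.31-fold for CV 50-100% and correlation 0.2-0.6. That understates lower VLN exposure and is unlikely to reverse it. The net effect for other patterns of residual and retained small values is not established, and no direction is claimed for AUC.

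**What to change.** 1. **SAP 9, Planned Tables and Listings:** derive and summarise unadjusted Cmax and AUC as the protocol states.
2. **SAP 5:** restore the protocol's PK-data condition for Completers, with no requirement that a parameter be estimable.
3. **SAP 9, rules:** state that BLQ is zero in the baseline adjustment and in the non-compartmental analysis, as it already is for descriptive statistics. State whether measurable refers to raw or adjusted values. State that non-positive adjusted parameters are excluded from the log model and counted per product.
4. **SAP 9, analyses:** keep the protocol AUC definition and the ratio model as the main analysis. Add to Tables 14.2.2.1.1-3 the n used and the counts of non-positive and non-estimable values. Add one sensitivity analysis that keeps every sampled profile, controlled and uncontrolled, with BLQ = 0 and AUC over the full session, using Hodges-Lehmann on untransformed within-subject differences. That method is already planned for Tmax and T1/2.
5. **SAP 12:** list any remaining departures from the protocol.

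The cost is SAP wording, extra columns in three shells, the parameter summaries already promised and one added analysis; no new data are needed. The sensitivity analysis gives a difference, not a ratio, so it checks the direction and size of lower exposure rather than the ratio itself. Setting BLQ to zero also overstates the own-brand minus VLN difference. In a check with no pre-use residual and a VLN peak of 2 or 4 x LLOQ, the overstatement was at most 0.3% (Cmax) and 2.8% (AUC) if own-brand is 20 times VLN, and at most 1.6% and 13.3% if it is 5 times. Profiles made negative by the subtraction, and the uncontrolled session, were not simulated in that check.

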#### Data Presentation and Precision

Individual raw PD VAS scores and PK concentrations will be displayed with the same precision as received as per lab data.

Precision for individual PD and PK parameters will be displayed as follow:

- $E_{\text{max}}$ ,  $C_{\text{max}}$  and AUCs with the same precision as the raw data
- PK parameters associated with time (e.g.  $T_{\text{max}}$ , and  $T_{1/2}$ ) with 2 decimal places
- $R^2$  and  $K_{\text{el}}$  with 4 decimal places

Summary statistics for VAS scores, PD parameters, PK concentration and parameters will be displayed with the same precision as the individual values, with the exception of CV% which will be presented with 1 decimal place and N with 0 decimal place.

#### Statistical Analysis of PK Parameters

A linear mixed model for analysis of variance (Proc Mixed) will be performed on the baseline-adjusted log transformed nicotine PK parameters in Part B ( $C_{\text{max}}(\text{controlled})$ ,  $C_{\text{max}}(\text{uncontrolled})$ ,  $AUC_{(\text{controlled})}$  and  $AUC_{(\text{controlled})}$ ). The model will include sequence, study product, and period as fixed effects and subject nested-within sequence as a random effect. Sequence will be tested using subject nested-within sequence as the error term. From each model, the geometric LSM and 95% confidence intervals will be calculated for each study product. Separate analyses will be performed on the parameters calculated for the Controlled and Uncontrolled Use sessions. Geometric mean ratios for each pair comparison, 95% confidence interval and p value will be provided.

The SAS codes for the model will be as follows:

```
Proc MIXED data=test;
  class subject sequence period product;
  model log(Cmax0_180) = sequence period product / ddfm=KR;
  random subject (sequence) / type=UN;
  estimate "Product A vs Product B" product 1 -1 0 /cl alpha=0.05;
  estimate "Product A vs Product C" product 1 0 -1 /cl alpha=0.05;
  estimate "Product B vs Product C" product 0 1 -1 /cl alpha=0.05;
  lsmeans product/cl alpha=0.05;
run;
```

The Hodges-Lehmann's method will be used to estimate the median differences and the 95% confidence interval of  $T_{\text{max}}$  and  $T_{1/2}$  between the products for controlled and uncontrolled use.

## 10. SAFETY

---

### Adverse Events

An adverse event (AE) is any untoward medical occurrence in a clinical investigation subject administered a product and may not necessarily have a causal relationship with the administered treatment. An AE can, therefore, be any unfavorable and unintended sign (including a clinically significant laboratory abnormality), symptom, or disease temporally associated with the use of an investigational product, whether or not related to the investigational product.

A study product use-emergent adverse event (SPUEAE) is defined as an AE that is starting or worsening at the time of or after study product administration (excluding product trial). An AE that occurs during the washout period between study products is considered study product use emergent to the last study product given.

SPUEAEs will be assigned to a product based on the time of occurrence in relation to the last product used prior to the onset of the SPUAE. SPUAEs will be assigned using the following rules:

- SPUAE will be assigned to the last product used by the subject where the date and time of the last product use is on or before of the start date and time of the event. Such assignment will be performed irrespective of any washout period between the start and stop dates of the SPUEAE.
- Any SPUEAE started after the discharge and during the follow-up period will be assigned to the last product that the subject has used during last cycle.

As an overall summary of AEs, the following will be presented by product use and overall in each part and by product use and overall regardless the study part:

- Number of reported AEs;
- Number and percentage of subjects experiencing AEs;
- Number of reported SPUEAEs;
- Number and percentage of subjects experiencing SPUEAEs;
- Number and percentage of SPUEAEs by relationship to study product;
- Number and percentage of SPUEAEs by severity;
- Number of reported study product use-emergent serious adverse events (SPUSAES);
- Number and percentage of subjects experiencing SPUSAES;
- Number and percentage of subjects experiencing SPUEAEs leading to discontinuation; and
- SPUEAEs with an outcome of death.

Frequencies of subjects with study product use-emergent AEs and incidence of those events, regardless of relationship to study product will be summarized by study product and sorted by system organ class. Frequencies of subjects with study product use-emergent serious adverse events and incidence of events will be likewise summarized. Frequencies of study product use-emergent adverse events will be summarized by severity and by relationship in separate tables.

Subject listings of all AEs including verbatim term, preferred term, study product, severity and relationship to study product will be provided. AEs leading to withdrawal and SAEs will also be presented in separate listings.

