7.1.3. End of Study or Early Termination

Subjects will be discharged from the clinic on Day 6 once all procedures are completed (or at Early Termination).

The maximum duration of subject participation, including Screening will be approximately 5 weeks.

An overview of the study design is provided in [Figure 1](#).

Study assessments and procedures will be performed at the visits and time points outlined in the Schedule of Assessments ([Table 1](#)).

^a In the event that the subject completes the cigarette in less than 10 puffs, no additional cigarette will be provided.

Figure 1: Overview of Study Design

[figure not shown]

Table 1: Schedule of Assessments

	Screening	Check-in	Part A	Part B								End of Study/ET	
Assessment	Day:	-28 to -2	-1	1 to 3	4 to 6 (Daily controlled use and uncontrolled use sessions)								
Informed consent		X			Assessment timepoints (minutes ^a)								
Demographics		X											
Medical history		X											
Review of eligibility		X	X										
Physical examination		X	X ^b										X ^b
Height, weight, BMI		X											
HIV, Hepatitis B/C		X											
Pregnancy test		X ^c	X ^d										
FSH (post-menopausal women)		X											
Vital signs ^e		X	X										X
Oral temperature		X	X										X
12-lead ECG		X											X
Urine cotinine screen		X											
Urine drug and alcohol test		X	X										

^a All listed timepoints are minutes after the start of product use

^b Abbreviated (symptom-directed) physical examination performed at the investigator's discretion

^c Serum pregnancy test

^d Urine pregnancy test

^e Vital signs include respiratory rate, pulse rate and blood pressure

	Screening	Check-in	Part A	Part B														End of Study/ET
Day:	-28 to -2	-1	1 to 3	4 to 6 (Daily controlled use and uncontrolled use sessions)														6
Assessment				Assessment timepoints (minutes ^a)														
Clinical laboratory tests ^f	X																	X
Concomitant medications	X	X	X		<----- Recorded throughout ----->													X
AE Monitoring ^g	X	X	X		<----- Recorded throughout ----->													X
Randomization			pre ^h	pre ⁱ														
Product use		X ^j	X ^k		<0 ^l	-	-	-	>									
PK sampling ^m				pre	2	5	7	10	12	15	20	30	45	60	90	120	150	180
Pharmacodynamic Training/practice ⁿ		X																
Tobacco/Nicotine Withdrawal Questionnaire ^o				pre		5				15		30		60	90			

^f Clinical laboratory assessments include hematology, biochemistry, and urinalysis

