10.3.1.3. Clinical Laboratory Abnormalities and Other Abnormal Assessments

Abnormal clinical laboratory findings (e.g., clinical chemistry, hematology, or urinalysis) or other abnormal assessments (e.g., from vital signs or ECG), judged as clinically significant by an investigator will be recorded as AEs or SAEs, if they meet the definitions provided previously. Abnormal laboratory or other findings present at baseline that significantly worsen following the start of the study will be reported as AEs or SAEs. However, abnormal findings present at the start of the study that do not worsen will not be reported as AEs or SAEs, unless an investigator or designee judges them as more severe than expected for the subject's condition.

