10.5. Appropriateness of Measures

The selection of abuse liability measures in this study, including the primary endpoints of “Urges to Smoke” and “Pleasant” E_{max} during the Controlled Use Session are consistent with previous studies of this type. The Use the Product Again VAS is being used as this is thought to indicate the subject’s willingness to use the product again and to reflect the user’s overall impression of the product. Other subscales of the Tobacco/Nicotine Withdrawal Questionnaire and the Direct Effects of Product Questionnaire will measure positive, negative and other subjective effects including craving to assess the subjective effects of the products for comparative purposes. Measures of product use behavior have been included during the ad libitum sessions and the Uncontrolled Use Sessions in order to evaluate the amount and duration of product used under both conditions.

Standard safety assessments have been included to evaluate the safety profile of VLN cigarettes. PK blood sampling has been included to evaluate the PK profile of nicotine following controlled and uncontrolled use of VLN cigarettes, in comparison with own-brand cigarettes and nicotine polacrilex gum.

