## APPENDIX A

### STUDY SCHEDULE

	Screening	Check-in	Part A	Part B												End of Study/ET		
Day:	-28 to -2	-1	1 to 3	4 to 6 (Daily controlled use and uncontrolled use sessions)												6		
Assessment				Assessment timepoints (minutes a )														
Informed consent	X																	
Demographics	X																	
Medical history	X																	
Review of eligibility	X	X																
Physical examination	X	X b														X b		
Height, weight, BMI	X																	
HIV, Hepatitis B/C	X																	
Pregnancy test	X c	X d																

NOTE: Pre-use assessments (not including PK) may be conducted up to 60 minutes prior to product use. When assessments coincide at any given timepoint during a product use session, the order of assessments should be pharmacodynamics assessments followed by PK. The pharmacodynamic assessments should be conducted at the nominal timepoint ( $\pm 2$  minutes up to 30 minutes postdose and  $\pm 5$  minutes postdose thereafter). AE=adverse event; BMI=body mass index; ECG=electrocardiogram; ET=early termination; FSH=follicle stimulating hormone; HIV=human immunodeficiency virus; pre=pre-use

a All listed timepoints are minutes after the start of product use

b Abbreviated (symptom-directed) physical examination performed at the investigator's discretion

c Serum pregnancy test

d Urine pregnancy test

	Screening	Check-in	Part A	Part B												End of Study/ET	
Day:	-28 to -2	-1	1 to 3	4 to 6 (Daily controlled use and uncontrolled use sessions)												6	
Assessment	Assessment timepoints (minutes a )																
FSH (post-menopausal women)	X																
Vital signs e	X	X															X
Oral temperature	X	X															X
12-lead ECG	X																X
Urine cotinine screen	X																
Urine drug and alcohol test	X	X															
Clinical laboratory tests f	X																X
Concomitant medications	X	X	X	<----- Recorded throughout ----->													X
AE Monitoring g	X	X	X	<----- Recorded throughout ----->													X
Randomization			pre h	pre i													

e Vital signs include respiratory rate, pulse rate and blood pressure

f Clinical laboratory assessments include hematology, biochemistry, and urinalysis

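### Adverse events first detected by the End of Study laboratory tests or ECG cannot be tied to a product day, yet by default the SAP counts them under the last product used

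*SAP*

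**What the plan says.** **Schedule.** Protocol Table 1 and SAP Appendix A mark the rows for "Clinical laboratory tests" and 12-lead ECG at Screening (Day -28 to -2) and at End of Study/ET. Neither row has a mark at check-in, in Part A or in Part B. A footnote defines the laboratory row: "Clinical laboratory assessments include hematology, biochemistry, and urinalysis". Vital signs have one further measurement, at check-in on Day -1.

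**Recording.** Protocol 10.3.1.3 says that abnormal laboratory, vital-sign or ECG findings "judged as clinically significant by an investigator will be recorded as AEs or SAEs, if they meet the definitions provided previously".

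**Assignment.** SAP section 10, Adverse Events, states the principle: "SPUEAEs will be assigned to a product based on the time of occurrence in relation to the last product used prior to the onset". The operative rule follows: "SPUAE will be assigned to the last product used by the subject where the date and time of the last product use" is no later than the event's start. There is no separate rule for an event known only from a comparison of Screening with End of Study.

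**Reporting.** Counts of subjects with product use-emergent events "will be summarized by study product and sorted by system organ class". Further tables split the same product columns by severity and by relationship.

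**Purpose.** Protocol 10.5 says: "Standard safety assessments have been included to evaluate the safety profile of VLN cigarettes".

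**The concern.** A last-product rule works when the onset of an event is observed, because the onset falls between two known product uses. It does not work for a finding whose only two scheduled measurements lie on either side of the whole exposure period. Between them, a subject who completes has used each of the three products on two separate days. The change could have begun on any of those six days, or even between Screening and Day 1.

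For these events the product column would reflect the randomised Part B order rather than the product responsible. A reader who uses the by-product tables to judge the safety of VLN cigarettes could take equal counts as evidence of no difference, when the assignment rule itself produces equality.

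**Working it through.** **1. How often the tests are done.** Protocol Appendix 17.1 gives an independent check on the schedule.

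- Pharmacokinetic samples: 15 time points × 2 sessions × 3 days = 90; 90 × 4 mL = 360 mL.
- Safety blood: 17.5 mL at Screening + 9 mL at End of Study = 26.5 mL.
- Total: 360 + 26.5 = 386.5 mL, which is the stated figure.
- Chemistry: 10 mL ÷ 5 mL = 2 draws. Hematology: 8 mL ÷ 4 mL = 2 draws.

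There is therefore one draw of each before product use and one after, with none in Part A or Part B. This agrees with Table 1.

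**2. Product days before the test.** Part A has 3 and Part B has 3, so 6 in all. The scheduled tests follow only the last, so 5/6 = 83% of product days have no scheduled laboratory test or ECG before the next product is used.

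**3. Product named by the rule on Day 6.** Part B has three sequences of about equal size (Protocol 9.3). With the planned minimum of 54 completers, each has 54 ÷ 3 = 18.

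| Part B sequence | Subjects | Day 6 product |
|---|---|---|
| ABC | 18 | C (gum) |
| BCA | 18 | A (VLN) |
| CAB | 18 | B (own-brand) |

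**4. Persistent abnormality.** Suppose one product causes a lasting abnormality in a fraction p of subjects, regardless of sequence. Each column then receives p × 18/54 = p/3. The correct product is named 1/3 of the time and a wrong one 1 − 1/3 = 2/3 of the time.

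The true rates below are assumed for illustration; the documents give none. Each column receives one third of the total.

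| Assumed true rates A / B / C | True events in 54 | Events assigned to each product |
|---|---|---|
| 10% / 10% / 10% | 5.4 / 5.4 / 5.4 | 16.2 ÷ 3 = 5.4 |
| 2% / 10% / 10% | 1.08 / 5.4 / 5.4 | 11.88 ÷ 3 = 3.96 |
| 2% / 20% / 2% | 1.08 / 10.8 / 1.08 | 12.96 ÷ 3 = 4.32 |

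**5. Same-day effect.** If an effect resolves before the next day's product, the Day 6 tests can detect it only in subjects who used that product on Day 6. The rule then names the correct product and the misassigned share is 0.

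The misassigned share thus runs from 0, when all effects are same-day, to 2/3, when all persist. The documents do not say which is nearer the truth.

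**The case against.** Five objections have force.

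- **Onset is not detection.** The rule uses the event's start, and no text equates that with the sampling time. Adverse events are monitored throughout, Protocol 10.3.3 allows extra laboratory samples at the investigator's discretion, and early terminators are tested at discontinuation (Protocol 8.3). A reader might infer that every laboratory or ECG event goes to the Day 6 product; the documents do not support that. The point is confined to events with no earlier onset recorded. For early terminators, the product named is the last one used before ET.
- **The values themselves are not misattributed.** SAP section 10 summarises laboratory and ECG results by visit, and the shells have a single Overall column. The listings of abnormal and clinically significant laboratory and ECG findings carry no product column. A signal would be visible there. This stands, and it limits the problem to the adverse-event tables.
- **The rule is a timing convention.** The investigator judges relationship separately, and the listing shows product and time since last use. That is correct, but the relationship table is itself laid out by product, so a rating of possible still appears under the Day 6 product.
- **No safety comparison is tested.** The product tables are descriptive, and safety is not among the primary or secondary objectives. This stands.
- **The cause is the design.** With one scheduled post-use test, no SAP rule can recover the missing information. That is true, but a rule can stop the tables from implying an attribution that the data cannot support.

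**Conclusion.** The point holds in limited form. For abnormalities first detected at the End of Study laboratory tests or ECG, with no earlier onset recorded, the product column is set by default by the Part B sequence. If they persist, about two-thirds are misassigned and the by-product counts move toward equality. This rests on balanced sequences and on the responsible product being unrelated to the Day 6 product.

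Three stronger readings are not supported:

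- **That the expected product difference is always zero.** This requires a fully persistent effect.
- **That the rule favours VLN.** It flattens differences in either direction.
- **That differential dropout gives some products more tests.** The documents contain no dropout figures by product.

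The number of affected events is not given and is probably small in screened healthy adults over six product days. The effect is confined to the by-product adverse-event tables and the product shown in the listings. The primary, pharmacokinetic and other inferential results are unchanged. The change is worth making because it is cheap and matches the SAP's own Overall presentation of laboratory and ECG values.

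**What to change.** Add one rule to the assignment rules in SAP section 10. An adverse event first identified from End of Study/ET laboratory or ECG tests, with no earlier onset recorded, is shown in a separate column, 'first detected at End of Study/ET - product not attributable', in Tables 14.3.1.1.x to 14.3.1.5.x. It stays in all totals, and the adverse-event listing continues to show the last product used and the time since last use.

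Keep last-product assignment for every event with an observed onset, including vital-sign events.

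A column is needed because moving these events to an Overall column would not work. The shells for system organ class and preferred term, serious events, severity and relationship (Tables 14.3.1.2.x to 14.3.1.5.x, 4 × 3 = 12 tables) have product columns only. The word Overall in their titles means both study parts combined, so the events would drop out of those tables.

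The cost is one SAP rule and one extra table column, with no new procedure. The drawback is that a few Day 6 events truly caused by the Day 6 product will leave the product columns; the listing still lets a reader identify them.
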